2. Loss of Confidentiality and Privacy: Confidentiality will be maintained by numerically coding all data, disguising identifying information, and keeping data locked in file drawers or in a secure, password protected database. All biospecimen samples are kept in a locked freezer and also will be deidentified. Names of participants will be kept separate from participant data. Only study research personnel and the PI will have the information that connects participants' names and ID numbers. All electronic data will be numerically coded and stored in a password-protected database, on a password-protected computer in a secure research space. Participant information will be accessible only to research staff, who are pledged to confidentiality and have completed training in the ethical conduct of research (i.e., both HIPAA and CITI trainings). Identifying information will not be reported in any publication.
3. Potential for Undermining Cessation: The study sample is comprised of smokers with no plan to quit in the next three months. Therefore, we are not asking smokers who want to quit to continue smoking. The PI will be available for any questions that participants may have about NPs, smoking, or smoking cessation. It is important to note that the use of NPs incurs no greater harm than if the participant decided on

his/her own to use the product. Among those screened and ineligible/uninterested, referral resources for smoking cessation will be provided for those who inquire.

Among study participants, information on cessation resources will be provided at the final visit and if at any time during the study participants are interested in smoking cessation services, a list of smoking cessation resources will be provided.

4. Slight risk of bruising, discomfort and infection with blood draw: Blood will be collected by trained research staff. Sterile instruments will be used and for blood draws, the participants skin will be cleaned with an alcohol wipe at the venipuncture site.

6. References

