Aim 1: This study will estimate the abuse liability of NPs with varying nicotine concentrations relative to cigarette smoking in a clinical study with Ohio Appalachian smokers by using a randomized crossover experimental design. Over the course of three clinic visits, N=40 adult cigarette smokers who live in Ohio Appalachia will: 1) smoke a usual brand cigarette, 2) use a 3mg nicotine concentration NP, and 3) use a 6mg nicotine concentration NP in our clinic; only one tobacco product will be used at each visit. We will measure nicotine pharmacokinetics, subjective effects, and intentions to use and switch to NPs. Our hypotheses are that (1a) both NPs will deliver less nicotine, and deliver it more slowly, than cigarette smoking and (1b) the 6mg nicotine NP will have greater nicotine delivery, be rated as more appealing, and have greater intentions for future use than the 3mg nicotine NP.

Aim 2: This study will examine the subjective and pharmacokinetic differences between tobacco-derived and synthetic NPs in adult cigarette smokers by using a randomized crossover experimental design. Over the course of three clinic visits, N=15 adult cigarette smokers who will: 1) use a 3mg tobacco-derived Zyn brand NP, 2) a 3mg synthetic Fre brand NP, and 3) a 3mg Niin brand synthetic NP in our clinic; only one product will be used at each visit. We will measure nicotine pharmacokinetics, subjective effects, and intentions to use and switch to NPs. Our hypotheses are that (1) tobacco-derived NPs will deliver nicotine more quickly and effectively than the synthetic NP and (2) the tobacco-derived NPs will be rated as more appealing and have greater intentions for future use than the synthetic NPs.

Intervention Impact

Aim 1: NPs are a novel tobacco product with potential to reduce or increase the harm of tobacco use in Appalachia. Evaluating NP abuse liability among Appalachian smokers will clarify the public health effect of NPs in Appalachian Ohio. Results will inform public health efforts, policy, and clinical care aimed at reducing tobacco-related disparities in Appalachia.

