This study will recruit 40 adult cigarette smokers from Ohio Appalachia and surrounding rural areas (Aim 1) and 20 adult cigarette smokers from Ohio (Aim 2) for a randomized crossover study. Subjects will be recruited through social media advertisements; through our nicotine pouch pilot study, where participants agreed to future contact regarding other studies; and through outreach to our community partners: the OSUCCC's Community Outreach and

Engagement team and the Tobacco Free Ohio Alliance. Subjects will have an initial phone screen to confirm interest and eligibility and will then be invited to participate in 3 study visits in person visits at the Center for Tobacco Research.

Aim 1: Order of study clinic visits will be randomized. In random order, participants will 1) smoke one usual brand cigarette, 2) use one 3mg NP, and 3) use one 6mg NP. Research staff will measure nicotine pharmacokinetics, subjective effects, and intentions to use and switch to NPs through physiological data, lab values, and questionnaires.

Aim 2: Order of study clinic visits will be randomized. In random order, participants will use 1) Zyn wintergreen 3mg (tobacco-derived nicotine) 2) a Fre wintergreen 3mg (synthetic nicotine), and 3) a Niin wintergreen 3mg (synthetic nicotine). Research staff will measure nicotine pharmacokinetics, subjective effects, and intentions to use and switch to NPs through physiological data, lab values, and questionnaires.

Recruitment phase

Aim 1: We will recruit daily cigarette smokers who live in Ohio Appalachia and surrounding rural areas using social media advertisements, by re-contacting participants from our preliminary studies who agreed to take part in future studies, and through outreach via our community partners.

Geographically, recruitment advertising will be targeted to Ohio Appalachia counties (32 in total), surrounding rural counties close to Ohio Appalachia, with efforts focused on counties within one hour of Columbus.

Aim 2: We will recruit daily cigarette smokers using social media advertisements, by re-contacting participants from our preliminary studies who agreed to take part in future studies, and through outreach via our community partners.

Participants in Aim 2 may reside anywhere in Ohio, though recruitment efforts will be focused within one hour of Columbus.

Screening and scheduling phase

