Schedule return visit per subject and interviewer availability that is >2 days after the current visit. Provide \$100 via Clincard for their participation out of the up to \$350 possible. If it is their last visit has been completed within 1 month from consent, they will receive \$150 during their last visit.

Post-Enrollment Survey

6 months after enrolling, participants from Aims 1 and 2 will be recontacted via phone, text, and email for the opportunity to participate in a short online REDCap survey. Participants will complete a short consent addendum and respond to survey questions regarding their current tobacco product use and opinions surrounding nicotine pouches. For their time, they will receive a \$10 Amazon gift code.

Procedure Manual

Study procedures, including conducting pregnancy tests, blood draws, blood processing and analysis, gift card administration, and other procedures will be thoroughly explained in the study procedure manual.

4. Study Administration

Randomization, Blinding, and Unblinding

Participants will be randomized within the secure database, REDCap. The randomization piece involves at which of the 3 visits they are to use each product (Aim 1: 3mg NP, 6mg NP, or their own usual brand cigarette and Aim 2: the tobacco-derived 3mg tobacco-derived NP or the 3mg synthetic pouches). Participants will be blinded during study visits and at the end of their third visit will be informed which product they had at each visit.

Study Timelines, Number of Sites, and Enrollment

Participant Timeline

There will be a total of 3 study visits and 1 online survey opportunity 6 months after the completion of the final study visit. The study timeline for each participant will vary. Clinic visits can be completed in as little as a week and a half or as long as 2 months, but will ideally be completed within 3 week's timeframe for retention and administrative purposes. The study visits will take approximately 3 hours each. The online survey will take approximately 10 minutes to complete and will be offered 6 months after completing the final visit.

Duration of Study

We anticipate the clinical trial to take six months to complete. After that, we anticipate that it will take 1-1.5 years to clean and analyze data and disseminate results.

Total Number of Study Sites

All recruitment and enrollment activities will be completed within the CTR.

Total Number of Subjects Projected

55 subjects will be enrolled and each subject must meet I/E criteria.

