Data Collection and Management

Data will be collected and stored electronically in the secure database, REDCap. Data will only be accessible to approved study personnel and will be secured through multiple firewalls. Subjects' first and last names will be deidentified and not linked with the data. The consent forms with first and last names will be databased electronically in REDCap but will not be downloaded with any study data.

Subject Completion, Withdrawal, and Early Termination

Participants will be invited to complete 3 study visits (i.e., participants cannot participate in both Aim 1 and Aim 2) and a supplemental, online survey opportunity to be completed once 6 months after the third clinic visit. The participant timeline will be complete once the 3 study visits are complete. Participants have the option to withdraw at any point by expressing their desire to withdraw to study staff orally or in writing. Study staff will complete a Withdrawal form to document this event. If at any point a participant becomes unable to complete study tasks per protocol (e.g., repeated violations of nicotine abstinence; inconsistent responses reported on questionnaires; showing up to a clinic visit impaired; injury, illness, or medications that impair ability to accurately complete study measures; or inappropriate behavior toward study staff), [name] reserves the right to ET a participant.

Informed Consent Process

Informed consent will be collected in person by a trained study staff member at the beginning of the initial study visit. Signatures will be documented electronically in REDCap and subjects will be offered an email or printed copy of the consent for their records.

For the 6-month follow on survey, an online consent addendum will be completed prior to the online survey. Signatures will not be collected for the consent addendum and instead the online framework of clicking "next page" will suffice.

Payment to Subjects

Participant compensation will be administered in two tiers: clinic visits and completion bonus.

Aim 1: For each clinic visit, subjects will receive \$150. If participants complete all three visits within a month, they will receive a \$50 bonus for their participation. Participants could earn up to \$500 for their participation. Compensation will be offered in the form of Clincard.

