Data will be summarized descriptively. For hypothesis testing, we will use linear or logistic mixed effects regression models (with a random subject effect) to assess the main effects of product on plasma nicotine delivery, subjective effects, and behavioral intentions. Model assumptions will be checked, and variables will be transformed as needed. Missing data will not be imputed as likelihood-based linear mixed models will yield valid inference under missing at random assumptions. Models will control for age, sex, and other tobacco use if these features are not balanced by randomization. The same analysis strategy will be used for both aims. We calculated power for Aim 1 based on a repeated measures ANOVA comparing mean total nicotine delivery and maximum plasma nicotine concentration across 3 conditions; existing literature on differences in nicotine delivery across SLT products, including NPs, facilitates the use of this outcome for a power analysis.⁹ With a total sample size of only 20 participants and a Bonferroni-adjusted alpha of 0.017, we would have 84% power to detect a mean difference in total nicotine delivery of 25.7 ng/mL and 99% power to detect a mean difference of maximum nicotine concentration of 7.0 ng/mL between products.⁹ To account for attrition and the potential need for a larger sample size to detect differences in more subjective outcomes, we will recruit a

sample of 40 participants. For Aim 2, there are no known data to estimate effect sizes and thus to conduct power analyses. The sample size of 15 participants is intended to provide these data for future research.

5. Safety Management, Risks, and Benefits

Safety Management

Clinical Adverse Events

Clinical AE will be assessed by study staff at each study visit via participant self-report and managed immediately. Clinical AE may be related to nicotine overdose or the blood draw. Signs of nicotine overdose include nausea, vomiting, headache, presyncope, tachycardia, and disrupted sleep. With the blood draw, there is a slight risk of bruising, discomfort, and infection with blood draw. Study staff will be trained to recognize these signs and subjects will be encouraged throughout the visit to self-report any AE. In the event of a medical emergency, study staff will be advised to call 911 on the subject's behalf.

AE Reporting

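### The Aim 2 sample size is 20 in the Study Outline but 15 in the aims and Statistical Considerations, and the projected total of 55 fits 40 + 15, not 40 + 20

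*Combined protocol and SAP*

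**What the plan says.** The Study Outline (section 2, Investigational Plan) sets recruitment for both aims in one sentence. It begins "This study will recruit 40 adult cigarette smokers from Ohio Appalachia and surrounding rural areas (Aim 1") and continues "and 20 adult cigarette smokers from Ohio (Aim 2) for a randomized crossover study".

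Elsewhere the Aim 2 figure is different:

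- Description and Rationale of Intervention, Aim 2: "N=15 adult cigarette smokers who will" attend three visits.
- Statistical Considerations (section 4): no effect-size data exist for Aim 2, so no power analysis was done. "The sample size of 15 participants is intended to provide these data for future research".
- Total Number of Subjects Projected (section 4): "55 subjects will be enrolled and each subject must meet I/E criteria".

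The Aim 1 figure does not vary. It is 40 in the Study Outline, 40 in the description of Aim 1 ("N=40 adult cigarette smokers who live in Ohio Appalachia will" attend three visits), and 40 in the Statistical Considerations. On overlap, the section on subject completion and withdrawal says "participants cannot participate in both Aim 1 and Aim 2".

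**The concern.** Two different enrolment targets for Aim 2 stand in the current text. Staff working from the Study Outline would enrol up to 20. Staff working from the Statistical Considerations or the projected total would stop at 15. Enrolling 20 in Aim 2 alongside a full Aim 1 would exceed the stated study total.

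The number also matters when the results are read. Aim 2 has no power calculation and no stated precision, so its sample size is the only design figure that says how much data it was meant to yield. Without one planned number, a later reader cannot tell whether 15 participants is full enrolment or a shortfall, or whether 20 is the plan or an overrun.

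**Working it through.** **Inputs**

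| Quantity | Value | Where |
|---|---|---|
| Aim 1 N | 40 | Description and Rationale of Intervention; Study Outline; Statistical Considerations |
| Aim 2 N | 20 | Study Outline |
| Aim 2 N | 15 | Description and Rationale of Intervention; Statistical Considerations |
| Projected total | 55 | Total Number of Subjects Projected |
| Overlap between aims | none allowed | Subject Completion, Withdrawal, and Early Termination |
| Aim 2 attrition rate | not stated | – |

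**Step 1: reproduce the plan's total.** With no overlap, total = Aim 1 N + Aim 2 N.

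- With 15: 40 + 15 = 55, which matches the stated total exactly.
- With 20: 40 + 20 = 60, which is 5 too many.

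The total is not broken down by aim, so this inference depends on Aim 1 being 40. All three statements of the Aim 1 figure agree on that.

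**Step 2: could 20 be an inflated recruitment target for 15?** If a proportion d is lost, the number to recruit is 15 / (1 − d). Setting this to 20 gives d = 1 − 15/20 = 0.25. The documents state no such rate for Aim 2. The only attrition allowance, "To account for attrition and the potential need for a larger sample size to detect differences in more subjective outcomes", belongs to the Aim 1 justification and leads to the 40. That 40 is counted in full in the 55.

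**Step 3: the other 20 in the document.** The Statistical Considerations also mention 20 participants, but as the sample size in the Aim 1 power calculation. It is not an Aim 2 target. Whether it is the source of the 20 in the Study Outline is conjecture.

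**Step 4: size of the discrepancy.**

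- 20 − 15 = 5 participants; 5/15 = 33%; 5/55 = 9%.
- The Aim 2 schedule has three visits, each with six draws (0, 5, 15, 30, 60 and 90 minutes). Five participants are up to 5 × 3 = 15 visits and 15 × 6 = 90 blood draws.

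**Step 5: precision, as an illustration only.** For one paired product contrast with complete data, the 95% half-width in units of the SD of the within-person difference is t(0.975, n − 1) / √n.

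- n = 15: 2.145 / 3.873 = 0.554
- n = 20: 2.093 / 4.472 = 0.468
- Ratio: 0.554 / 0.468 = 1.18

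The documents do not give that SD, so these cannot be turned into ng/mL.

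**The case against.** The best defence is that the two figures count different things. The Study Outline speaks of recruiting, and then describes a phone screen for eligibility. The projected total speaks of subjects enrolled who meet the criteria. On that reading, 20 would be approached so that 15 could be enrolled. The difference in verbs is real, but the documents never draw this distinction. The same sentence uses the same verb for the 40 in Aim 1, which is the final sample size elsewhere and enters the total without reduction. If the distinction were intended, it would still have to be written down.

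The second argument is about weight, and much of it stands. Three of the four places point to 15, including the section that sets the sample size, so this looks like a single wrong number in an outline sentence. No power, alpha or precision statement depends on it. The extra visits and draws arise only if 20 people are actually enrolled. The half-widths assume a paired analysis with complete data, whereas the plan is a mixed model that also uses incomplete data. They show the scale of the difference and do not contradict any promise in the plan.

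Finally, the stated total is not itself miscalculated. The defect is a conflict between sections that the addition exposes.

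**Conclusion.** The concern holds. The Study Outline's 20 for Aim 2 conflicts with the 15 given in the aims and the Statistical Considerations, and with the total of 55. The gap is five participants, or 60 against 55. The conclusion rests on two things the documents state: Aim 1 is 40 throughout, and the aims share no participants. Nothing in the text reconciles the figures.

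The balance of the text favours 15, but only the investigators can say which number was planned. This should be corrected because it is an enrolment target. It does not invalidate any analysis or power claim.

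**What to change.** State one Aim 2 sample size throughout.

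- **If 15 is the plan**, change 20 to 15 in the Study Outline. This is one number in one sentence. It adds no participants and leaves the total at 55.
- **If 20 is the plan**, change 15 to 20 in the Description and Rationale of Intervention and in the Statistical Considerations, and change the projected total to 60. This is three numbers, and five more participants than the stated total, with up to 15 more visits and 90 more blood draws.
- **If 20 was meant as a number to approach and 15 as a number to enrol**, say so in the Study Outline, with the assumed loss. Going from 20 to 15 implies 25%.

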Interested participants will fill out a brief questionnaire to confirm eligibility either online or over the phone with research staff. Participants will be asked a series of questions regarding their tobacco product usage, health status, willingness to travel to Columbus for study visits, and brief demographic and contact information. Research staff will review the screener questionnaire for eligibility and inform participants if they are eligible for this study or not. Research staff will provide a study overview, discuss study procedures, and ascertain participant interest. Should the participant wish to proceed, research staff will schedule the first visit and communicate IRB-approved guidance, such as the CTR address and the need for subjects to abstain from tobacco products for 12 hours prior to the study visit. Participants will be advised that each research visit must be scheduled 2 or more days apart and that they must bring their own brand of cigarettes to the study visits in case they are randomized to smoke cigarettes at a particular visit.

Clinic Visits

Aim 1: Participants will be invited to the CTR to complete study procedures. At visit 1, informed consent will be collected. During visits 1-3, participants will complete an exhaled CO test, take a pregnancy test if applicable, a line will be placed for IV blood draw by the staff research nurse for IV blood draws throughout the course of the study visit, and be asked to either smoke their usual brand or insert a 3mg or 6mg NP and then sit in the room for 60 minutes. At each visit, participants will be randomly assigned to use 3mg Wintergreen pouches, 6mg Wintergreen pouches or their own brand of cigarettes. Participants will be asked a series of 3 questionnaires before, during, and after each product is used. Blood draws will be collected from the line at 0 5, 15, 30, 60, and 90-minutes. 3mLs, or a little less than 1 teaspoon, of blood will be drawn at each timepoint.

Measures of craving and withdrawal relief will be assessed at each blood draw (see attached surveys). If a collection interval is not met there will be no draw retroactively. Participants will be assessed for AE throughout procedures and prior to leaving the visit.

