Aim 2: Adults aged 21 and older who reside in any Ohio county and smoke at least 5 cigarettes per day will be considered for this project. Smokers who use other tobacco products (e.g., SLT, electronic cigarettes) > 10 days a month will be ineligible because our goal is to characterize the abuse liability of NPs among those who exclusively or primarily smoke cigarettes.

Inclusion	Exclusion
Age 21 years or older	Use tobacco products other than cigarettes >10 days per month.
Willing to complete study procedures, including abstaining from all tobacco, nicotine, and marijuana for 12 hours before clinic visits	Use NP in the past 3 months
Ability to read and speak English	Unstable or significant psychiatric conditions (past and stable conditions will be allowed)
Smoke at least 5 cigarettes per day for the past 30 days	Pregnant, planning to become pregnant, or breastfeeding
	History of cardiac event or distress within the past 3 months
	Currently attempting to quit all tobacco use

3. Study Procedures

Clinic Visits

Informed consent

The participant will arrive at the CTR and meet a member of the research staff in the lobby. The research staff member will escort the subject to a private lab room and review the informed consent form (including a description of the nature, purpose, risks, and benefits of the study). The subject will receive an oral and written explanation of the study. The voluntary nature of the study and the participant's right to withdraw at any time will be stressed during the consent process; a copy of the informed consent will be provided to the participant either electronically or physically at the time of consent for them to keep. Informed consent will be collected by IRB-approved study personnel and stored electronically in the secure database, REDCap.

Recruitment scripts and materials, consent forms, and all study procedures will be approved by the OSU Institutional Review Board. All participants will provide written consent before any study procedures are performed.

Randomization

After participants consent to the study, their visit order will be randomized. Randomization will be counterbalanced and cannot be changed once it is completed. Randomization in Aim 1 involves the 3mg, 6mg, or regular brand of cigarettes while Randomization in Aim 2 involves the 3mg tobacco-derived NP and 2 synthetic NPs.

Obtain baseline exhaled CO test

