Participants will need to abstain from tobacco and nicotine products for ≥ 12 hours prior to their study visit. To check for abstinence from tobacco, participants will perform exhaled carbon monoxide testing ($eCO < 10\text{ppm}$) and confirm via self-report that they have not used any other nicotine products over the last 12 hours.

Pregnancy Test

All subjects capable of becoming pregnant will need to take and produce a negative pregnancy test in order to proceed further.

Pre-intervention questionnaire to be administered

This questionnaire will assess sociodemographics, tobacco use history, NP use history, and nicotine dependence. These questionnaires will be administered during Visit 1.

IV line insertion

Because blood draws will occur at set intervals, an IV line will be inserted by a trained staff nurse.

Blood draw to obtain baseline plasma nicotine levels

Next, participants will be reminded that in addition to the exhaled CO test, their abstinence will be confirmed at the time of visit via blood plasma nicotine analysis. 3 mL venous blood sample will be collected for later analysis to confirm abstinence. This blood draw will also be used to establish baseline plasma nicotine levels to estimate total nicotine delivery.

Administer intervention

Aim 1: The participant will receive a 3mg NP, 6mg NP, or be asked to smoke one cigarette of their usual brand depending on the randomization assignment. If smoking a cigarette, participants will be asked to smoke one cigarette following a standardized puffing protocol: they will take one puff every 30 seconds for 5 minutes. If using an NP, participants will be asked to place the pouch between their upper lip and gum and leave it in place for 30 minutes.

Aim 2: The participant will receive a 3mg tobacco-derived NP or a 3mg synthetic NP on randomization assignment. Participants will be asked to place the pouch between their upper lip and gum and leave it in place for 30 minutes.

Peri-intervention questionnaire to be administered

The QSU and MNWS surveys will be administered while at each blood draw interval of 0, 5, 15, 30, 60, and 90 minutes.

Post-intervention questionnaire to be administered

Measures of product appeal and behavioral intentions will be assessed after the participant has the cigarette or NP (Aim 1) or the tobacco-derived vs. synthetic NP (Aim 2).

Schedule return visit and provide gift card for participation

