Aim 2: For each clinic visit, subjects will receive \$100. If participants complete all three visits within a month, they will receive a \$50 bonus for their participation. Participants could earn up to \$350 for their participation. Compensation will be offered in the form of Clincard.

If any part of the visit is not possible to complete, participants will be given \$50 to thank them for their time.

Aims 1 & 2: 6 months after the final visit is complete, participants from Aim 1 and 2 will be offered participation in a short, 10-minute online survey via email. For their time, participants will receive a \$10 Amazon gift code within 2 business days via email.

Confidentiality

Confidentiality will be maintained by all study staff along with the use of a secure study database.

All lab personnel and study staff will complete HIPAA and CITI trainings, human subjects protection training, responsible conduct of research training, and good clinical practices training. Phone scripts will be developed to ensure the subject is in an isolated environment where they are comfortable sharing personal information during the phone screen. During the study visit, participants will be taken to a private lab environment.

The secure databasing platform, REDCap, will store participant data. A subject ID will be assigned to each participant in order to deidentify study data. Multiple levels of security clearance are required before entering the REDCap system and only approved study personnel will have access to this data.

Compliance Statement

Research will be conducted in accordance with CTR policies and IRB regulations. Questions will be directed to OSU IRB representatives and S/AEs will be reported per IRB policy.

Statistical Considerations

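### Visit order is randomised before the visit 1 pregnancy test, CO check and IV placement, so a participant permanently lost at those steps uses up a counterbalanced order and gives no data

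*Combined protocol and SAP*

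**What the plan says.** Under Clinic Visits in section 2, consent belongs to the first clinic visit: "At visit 1, informed consent will be collected". Section 3 then lists the steps in this order: consent, randomisation, CO test, pregnancy test, baseline questionnaire, IV line, baseline blood draw, product use. On randomisation it says: "After participants consent to the study, their visit order will be randomized. Randomization will be counterbalanced and cannot be changed once it is completed".

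Two checks follow the allocation:
- **Pregnancy test.** This is a hard stop: "All subjects capable of becoming pregnant will need to take and produce a negative pregnancy test in order to proceed further". Pregnancy is also an exclusion criterion in both aims.
- **CO check.** "To check for abstinence from tobacco, participants will perform exhaled carbon monoxide testing", with a threshold of 10 ppm. The consequence of failing is not stated.

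Both recur at each visit: "During visits 1-3, participants will complete an exhaled CO test, take a pregnancy test if applicable".

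Elsewhere, the section on withdrawal and early termination allows discretionary removal and gives as one example "repeated violations of nicotine abstinence". Payment to Subjects provides a part payment for the case "If any part of the visit is not possible to complete". Statistical Considerations specifies mixed models for product with a random subject effect, adjusted for age, sex and other tobacco use if these are unbalanced. It names no period or sequence term. The documents do not give the number of orders, the block size, a replacement rule or an expected failure rate at visit 1.

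**The concern.** In a three-period crossover, counterbalancing keeps each product's average visit number nearly equal, so that drift over visits (familiarity with the clinic, adaptation of ratings) cancels out of the product comparisons. An order given to someone who never uses a product does not contribute to that cancellation. Such a person is also randomised, has no outcome data and, if pregnant, is ineligible.

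The model as named does not recover the lost balance, because visit is not in it. With 15 participants in Aim 2, a few lost orders are a noticeable share of the list.

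**Working it through.** **Inputs from the documents.** Aim 1 has 40 participants. Aim 2 has 15 (Description and Rationale; Statistical Considerations; the total of 55 agrees), although Study Outline says 20. There are three products, hence six possible orders. The plan has no figure of its own on this point to reproduce. Its power statement cannot be rebuilt, because no SD is given, and nothing here depends on it.

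**Assumptions.** Permuted blocks of six orders; permanent loss at visit 1 at random with probability p = 0, 5, 10 or 20%; lost orders not reused.

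**Step 1: measure of balance.** For each participant let d be the visit number of product A minus that of product B. Over the six orders d takes the values −2, −1, −1, 1, 1, 2, with mean 0 and variance 12/6 = 2. Let D be the average of d over retained participants. If the outcome drifts by δ per visit and visit is not modelled, the A−B contrast is shifted by D × δ.

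**Step 2: no losses.** Complete blocks sum to zero. Only the r participants left over in the last block matter, and the sum of d has variance V = 2r(6 − r)/5.
- N = 15: r = 3, V = 3.6, RMS of D = √3.6/15 = 0.126.
- N = 40: r = 4, V = 3.2, RMS of D = √3.2/40 = 0.045.

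Exact balance is therefore impossible with six orders even without losses (15/6 = 2.5; 40/6 = 6.67).

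**Step 3: with losses.** Given m retained out of N,

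E[D² | m] = 2/m − (2N − V)(m − 1) / [m N (N − 1)],

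which is averaged over m ~ Binomial(N, 1 − p). At the expected m for 20% loss:
- N = 15, m = 12: 2/12 − 26.4 × 11/(12 × 210) = 0.0514, square root 0.227.
- N = 40, m = 32: 2/32 − 76.8 × 31/(32 × 1560) = 0.0148, square root 0.122.

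Averaged over m, the RMS of D is:

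| Permanent loss | N = 15 | N = 40 |
|---|---|---|
| 0% | 0.126 | 0.045 |
| 5% | 0.155 | 0.069 |
| 10% | 0.182 | 0.089 |
| 20% | 0.234 | 0.123 |

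A separate simulation (4,000 runs per scenario) agrees to within 0.003.

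**Step 4: chance that any order is lost,** 1 − (1 − p)^N. At 5, 10 and 20% this is 54, 79 and 97% with 15 participants, and 87, 99 and over 99% with 40.

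**Step 5: sensitivity (same simulation, losses of 5/10/20%).**
- Three orders instead of six: N = 15 goes from 0 to 0.089/0.132/0.195; N = 40 from 0.035 to 0.064/0.086/0.121.
- Failures replaced from the next list slot, six orders: 0.141/0.152/0.182 with N = 15 and 0.059/0.080/0.106 with N = 40. Replacement helps but does not restore the no-loss value.

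**Step 6: what it does to the contrast.** Take an assumed drift of half a residual SD (σ) per visit. At N = 15 with 20% loss, the shift has RMS 0.5 × 0.234 = 0.117σ. The sampling error of a pairwise contrast with 12 participants is σ√(2/12) = 0.408σ. Combined: √(0.408² + 0.117²) = 0.425σ, about 4% larger. With no loss the same drift adds about 1.5% (0.063σ against 0.365σ).

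**Step 7: bias and false positives.** The mean of D is zero by symmetry. The model without a period term was simulated with no product effect and drift of 0.25, 0.5 and 1.0 σ per visit (6,000 runs each). Pairwise type I error at a nominal 5% lay between 0.6% and 4.5% for both sample sizes, with 0% and with 20% loss.

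**The case against.** The strongest case against the point is that very little may be lost, and four stronger readings do go too far.

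- **The vacated order is gone for good.** The bar on changing a completed randomisation most naturally fixes a participant's own order. The documents neither forbid nor provide for giving that order to someone else.
- **A failed CO check ends participation.** No such consequence is stated. Early termination is discretionary and its example is repeated violations, which suggests that one failure can be tolerated. A participant who is rebooked keeps the order, and nothing is lost.
- **The product contrast is biased.** These losses happen before any product use. If they are unrelated to order, the imbalance averages zero, and unmodelled drift also enlarges the residual error, so the tests are conservative. Random order itself protects against systematic visit effects; what weakens is the extra tightness from counterbalancing.
- **A loss of 20% is to be expected.** No rate appears in the documents, and health status is screened before visit 1, so the one explicit stop may seldom occur.

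Aim 2 is also meant only to supply data for future research, and a procedure manual that is not among the documents may cover failed checks.

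All of this stands and limits the size of the effect. It does not remove the facts that one exclusion criterion is verified after allocation, that no reuse rule is stated, and that the model lacks a visit term. Nor does the early allocation bring a visible benefit: no step between consent and product use needs the assignment, and Aim 1 participants are told to bring their cigarettes to the visits in any case.

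**Conclusion.** The point holds as a minor design improvement. Anyone permanently lost between randomisation and product use at visit 1 is randomised without data and has used a counterbalanced order. The harm is wasted allocations and a modest loss of balance and precision. At an assumed 5 to 20% loss, the RMS imbalance stays below a quarter of a visit in Aim 2 and at about an eighth or less in Aim 1.

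These sizes rest on assumed blocks of six orders, assumed loss rates and losses at random. They matter only if outcomes drift across visits. A reader might infer biased product effects or inflated false-positive rates; the check supports neither.

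**What to change.** 1. Move the REDCap randomisation step to after the visit 1 CO check, pregnancy test and IV placement, immediately before product use. Keep the rule that it cannot be changed from that point on. This reorders one step, costs no participants or data, and brings imbalance from visit 1 failures back to the no-loss row of the table.
2. Include visit (period) as a fixed effect in the mixed models. The same checks recur at visits 2 and 3, where the first change prevents nothing; a period term removes additive visit effects whichever visit causes the loss. With complete data it costs two residual degrees of freedom: 28 to 26 with 15 participants, 78 to 76 with 40.
3. State in the protocol the number of orders, the block size, how a vacated order is handled and what follows a failed CO check. Reconcile the Aim 1 Clinic Visits wording, which describes random assignment at each visit, with the single randomisation of visit order in section 3, and settle the Aim 2 sample size (15 or 20). This costs only text.
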